3.3.6 Definition of baseline

In general, the last non-missing measurement on or prior to the date of randomization will serve as the baseline measurement for efficacy variables. If there is no value on or prior to the date of randomization, then the baseline value will not be imputed, and will be set to missing.

In general, the last non-missing measurement prior to first dose of study treatment will serve as the baseline measurement for safety and pharmacokinetic variables. If there is no value prior to first dose of study treatment, then the baseline value will not be imputed, and will be set to missing.

3.3.7 Change from baseline

Change from baseline is defined as

$$(\text{post-baseline value} - \text{baseline value})$$

If either the post-baseline value or the baseline value is missing, then the change from baseline will also be missing.

4 STATISTICAL ANALYSIS

This section provides information on definitions, derivation and analysis/data presentation per domain.

4.1 Study Population

The domain study population covers participant disposition, analysis sets, protocol deviations, demographics, baseline characteristics, medical history, prior and concomitant medications and study drug compliance.

4.1.1 Patient Disposition and Completion Status

4.1.1.1 Definitions and Derivations

Screen failures are defined as participants who complete informed consent/assent to participate in the clinical study but are not subsequently randomly assigned to study intervention.

4.1.1.2 Presentation

Participant disposition will be summarized using the all participants analysis set. The number of participants screened will be summarized. The number and percentage of participants within each treatment group will be presented by the following categories: randomized, randomized but not treated (and reason), started treatment, completed treatment, discontinued treatment (and reason), completed study, and withdrawn from study. Participant recruitment by center will also be summarized.

4.1.2 Analysis Sets

4.1.2.1 Definitions and Derivations

See section [0](#) for full definitions of the analysis sets.

4.1.2.2 Presentation

The number and percentage of participants in each of the analysis sets will be summarized by treatment group, along with reason for exclusion for participants not included in each set. Refer to [Table 1 Populations for Analysis](#) for full definitions of each analysis sets.

4.1.3 Protocol Deviations

4.1.3.1 Definitions and Derivations

See section [3.3.5](#) for definition of IPDs.

4.1.3.2 Presentation

IPDs will be summarized for the full analysis set, by treatment group and overall. All COVID-19 related IPDs will be summarized together with all non-COVID-19 related IPDs, along with an additional summary of IPDs related to COVID-19, and IPDs excluding COVID-19 related IPDs separately.

A listing of all COVID-19 related PDs (important and non-important PDs) will be provided.

4.1.4 Demographics

4.1.4.1 Definitions and Derivations

Demographic data will include age at time of informed consent, sex, race, and ethnicity. Age will be summarized both continuously and by group, split by the stratification factors: ≥ 12 to < 18 and ≥ 18 to ≤ 21 .

4.1.4.2 Presentation

Demographics will be summarized by treatment group and presented for the full analysis set, and the vaccine immunogenicity analysis set if applicable, as detailed in section [0](#).

4.1.5 Baseline Characteristics

4.1.5.1 Definitions and Derivations

Baseline characteristics (weight [kg], height [cm], and body mass index (BMI) [kg/m^2]) are collected at visit 1.

4.1.5.2 Presentation

Baseline characteristics will be summarized by treatment group and presented for both the full analysis set and the vaccine immunogenicity analysis set if applicable, as detailed in section [0](#).

4.1.6 Disease Characteristics

4.1.6.1 Definitions and Derivations

Disease characteristics will include, but is not limited to; smoking status, history of allergy, asthma medications, the number of asthma exacerbations in the previous 12 months, number of asthma exacerbations requiring hospitalizations in the previous 12 months, and CCI [REDACTED].

Baseline lung function is collected at either visit 1 or visit 2, and is assessed for both pre- and post-bronchodilator spirometry. Measures include Forced Vital Capacity (FVC) (L), FVC (%), Forced Expiratory Volume in 1 second (FEV1) (L), FEV1 (% of predicted normal), FEV1 reversibility (L), FEV1 reversibility (%), and FEV1/FVC Ratio (%). Historical reversibility will be listed, where available.

4.1.6.2 Presentation

Disease characteristics will be summarized by treatment group and presented for both the full analysis set and the vaccine immunogenicity analysis set if applicable, as detailed in section 0.

4.1.7 Medical History and Concomitant Disease

4.1.7.1 Definitions and Derivations

Medical and surgical histories are reported at screening.

4.1.7.2 Presentation

Medical and surgical histories will be summarized by treatment group and Medical Dictionary for Regulatory Activities (MedDRA) Preferred Term (PT) within the System Organ Class (SOC) level of MedDRA, and will be presented for the full analysis set.

4.1.8 Prior and Concomitant Medications

4.1.8.1 Definitions and Derivations

A list of permitted, restricted and prohibited medications can be found in section 6.5 of the CSP. Please refer to [Appendix B: Imputation Rules for Missing/Partially Missing Prior/Concomitant Medication](#) for the method of imputation of missing concomitant medication onset/start and end/stop dates.

Medications will be categorized for analysis according to their onset and end dates as follows:

- Prior medications:
 - end date \leq date of first dose of study intervention
- Concomitant medications during on-treatment period:
 - end date $>$ date of first dose of study intervention and start date \leq minimum (date of last dose of study intervention + 33 days, date of death, date of study withdrawal), or
 - end date ongoing and start date \leq minimum (date of last dose of study intervention + 33 days, date of death, date of study withdrawal)
- Concomitant medications during post-treatment period (for subjects still being followed up then):

- start date > date of last dose of study intervention + 33 days.

4.1.8.2 Presentation

Prior, concomitant and disallowed medications will be summarized by their Anatomical Therapeutic Chemical (ATC) classification system codes and generic name, by treatment group. Each will be presented for the full analysis set. On-treatment and post-treatment concomitant medications will be summarized separately.

4.1.9 Study Drug Compliance

4.1.9.1 Definitions and Derivations

Treatment compliance will be calculated as follows:

$$Treatment\ compliance\ (\%) = \left(\frac{\text{total number of actual dosing occasions}}{\text{total number of expected dosing occasions}} \right) \times 100$$

In order to allow for participants who discontinue study intervention early or who receive additional doses due to delayed flu vaccine administration, in the compliance calculation, the number of expected dosing occasions will be calculated as the number of dosing visits up to and including the last available dosing visit for that participant.

4.1.9.2 Presentation

Treatment compliance will be summarized by treatment group and presented for the full analysis set. The date and time of study intervention administrations, and all missed doses will be listed.

4.2 Endpoint Analyses

This section covers details related to the efficacy endpoint analyses such as primary, secondary, other endpoints including sensitivity and supportive analyses. Table 2 gives details of the primary analysis estimands.

Table 2 Primary Analysis Estimands and Endpoints

Primary Endpoints	Parameters

 Post-vaccination strain-specific HAI antibody GMFRs from Week 12 (pre-vaccination antibody measure) to Week 16 (EOT) Post-vaccination strain-specific MN antibody GMFRs from Week 12 (pre-vaccination antibody measure) to Week 16 (EOT) Post-vaccination strain-specific serum HAI antibody GMTs obtained at Week 16 (EOT) Post-vaccination strain-specific serum MN antibody GMTs obtained at Week 16 (EOT) 	
Population: Vaccine immunogenicity analysis set, defined as all randomized participants who received the influenza vaccine plus at least 1 dose of tezepelumab or placebo, had pre-vaccination and post-vaccination HAI or MN antibody measurements, had no influenza infection prior to Visit 7 (Week 16), and had no protocol deviation judged to have the potential to interfere with the generation or interpretation of an antibody response.
 
Intercurrent Events:
 
Treatment discontinuation: All data up to timepoint of post-vaccination antibody measurements will be included for participants in the vaccine immunogenicity analysis set.
 
Initiation of any other medication: All data up to timepoint of post-vaccination antibody measurements will be included for participants in the vaccine immunogenicity analysis set.
 
Summary Measure: Least square geometric mean ratio estimates for placebo vs. tezepelumab and corresponding 90% confidence intervals (CIs).


 Post-vaccination strain-specific antibody response at EOT with antibody response defined as a ≥ 4-fold rise in HAI antibody titer from Week 12 (pre-vaccination antibody measure) to Week 16 (EOT) Post-vaccination strain-specific antibody response at EOT with antibody response defined as a ≥ 4-fold rise in MN antibody titer from Week 12 (pre-vaccination antibody measure) to Week 16 (EOT) Post-vaccination strain-specific HAI antibody titer ≥ 40 at Week 16 (EOT) Post-vaccination strain-specific MN antibody titer ≥ 40 at Week 16 (EOT) 	
Population: Vaccine immunogenicity analysis set, defined as all randomized participants who received the influenza vaccine plus at least 1 dose of tezepelumab or placebo, had pre-vaccination and post-vaccination-dose HAI or MN antibody measurements, had no influenza infection prior to Visit 7 (Week 16), and had no protocol deviation judged to have the potential to interfere with the generation or interpretation of an antibody response.
 
Intercurrent Events:
 
Treatment discontinuation: All data up to timepoint of post-vaccination antibody measurements will be included for participants in the vaccine immunogenicity analysis set.
 
Initiation of any other medication: All data up to timepoint of post-vaccination antibody measurements will be included for participants in the vaccine immunogenicity analysis set.
 
Summary Measure: Number and % of participants in each treatment group meeting the specified threshold and corresponding 90% CI.

4.2.1 Primary Endpoint

4.2.1.1 Definition

The primary objective is to evaluate the effect of tezepelumab on the humoral immune response following seasonal influenza virus vaccination in adolescent and young adult participants with moderate to severe asthma.

The primary endpoints are defined as follows:

- Post-vaccination strain-specific HAI antibody GMFRs from Week 12 (pre-vaccination antibody measure) to Week 16 (EOT).
- Post-vaccination strain-specific MN antibody GMFRs from Week 12 (pre-vaccination antibody measure) to Week 16 (EOT).
- Post-vaccination strain-specific serum HAI antibody GMTs obtained at Week 16 (EOT).
- Post-vaccination strain-specific serum MN antibody GMTs obtained at Week 16 (EOT).
- Post-vaccination strain-specific antibody response at Week 16 (EOT) with antibody response defined as a \geq 4-fold rise in HAI antibody titer from Week 12 (pre-vaccination antibody measure) to Week 16 (EOT).
- Post-vaccination strain-specific antibody response at Week 16 (EOT) with antibody response defined as a \geq 4-fold rise in MN antibody titer from Week 12 (pre-vaccination antibody measure) to Week 16 (EOT).
- Post-vaccination strain-specific HAI antibody titer \geq 40 at Week 16 (EOT).
- Post-vaccination strain-specific MN antibody titer \geq 40 at Week 16 (EOT).

As the HAI assay may not work for one of the influenza virus strains (Influenza A H3N2), the corresponding MN result for that strain will only be used, please see CSP for more details on the influenza virus strains. Hence, both the HAI and MN results will serve as the dual primary endpoints for this study such that results from both assays can be used for the analyses of the primary objective. This dual endpoint approach allows for a broader characterization of the immune response and flexibility in case the results for either assay are missing. The analyses of the primary endpoints will be summarized separately for each influenza virus strain, using the vaccine immunogenicity analysis set.

4.2.1.2 Derivations

Geometric mean fold rises for the HAI and MN antibody measurements are defined as:

$$\text{GMFR} = \text{antilog}_e (\text{mean} [\log_e x])$$

Where x is the post-vaccination (EOT) HAI or MN antibody titer fold rise from Week 12 (pre-vaccination antibody measure) and e is the natural logarithm.

Geometric mean titers for the HAI and MN antibody measurements are defined as:

$$\text{GMT} = \text{antilog}_e (\text{mean} [\log_e y])$$

Where y is the HAI or MN antibody titer and e is the natural logarithm.

For HAI & MN assay results reported as lower than the lower limit of quantification (LLOQ), a value equal to half of the LLOQ will be imputed and used for analysis purposes.

4.2.1.3 Handling of Dropouts and Missing Data

If informed consent/assent to the study was withdrawn, all data up until the date of withdrawn informed consent/assent will be included.

4.2.1.4 Primary Analysis of Primary Endpoint

Geometric mean fold rises and GMTs will be summarized by influenza virus strain and treatment group, and the least square geometric mean ratio of GMFRs and GMTs between treatment groups (influenza vaccine divided by tezepelumab and influenza vaccine) will be calculated via an analysis of covariance (ANCOVA) model on the log-transformed variable, adjusting for treatment group and age stratum (adolescents aged 12 to 17 or young adults aged 18 to 21). The least square geometric mean ratio and mean difference will be provided with associated 90% CIs. The results of this analysis will also be presented in forest plots.

The antibody response to the influenza vaccine is defined as a \geq 4-fold rise in HAI or a \geq 4-fold rise in MN from Week 12 (pre-vaccination antibody measure) to Week 16 (EOT). The proportion of participants who experience a post-vaccination antibody response at Week 16 (EOT) for HAI and the proportion of participants who experience a post-vaccination antibody response at Week 16 (EOT) for MN and corresponding 90% Clopper-Pearson exact CIs ([Clopper et al 1934](#)) will be summarized by treatment group.

The proportion of participants who achieve a post-vaccination HAI antibody titer ≥ 40 and the proportion of participants who achieve a post-vaccination MN antibody titer ≥ 40 at Week 16 (EOT) and corresponding 90% Clopper-Pearson exact CIs will be summarized by treatment group.

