Participants with moderate to severe asthma will be randomized 1:1 to receive tezepelumab 210 mg or placebo SC Q4W, administered at Weeks 0, 4, 8 and 12. Enrollment into screening will be monitored to ensure at least 50% of the randomized participants are between the ages of 12 to 17 years. Treatment allocation will be stratified by age at the time of informed consent/assent (12 to 17 years, and 18 to 21 years) to ensure equitable distribution of tezepelumab and placebo treatment in each age group.

Please note: If influenza vaccine administration is delayed, the treatment period may be extended and therefore participants may be given an additional 1 to 2 study intervention doses (as needed) every 4 weeks for a longer period than initially planned.

Data Monitoring Committee: No

Statistical Methods

Primary Endpoints

For the analysis of the anti-influenza antibody response endpoints, GMFRs and GMTs for HAI and MN antibody measurements will be summarized by treatment group and by strain, and the least square geometric mean ratio of GMFRs and GMTs between treatment groups (influenza vaccine divided by tezepelumab and influenza vaccine) will be calculated via an ANCOVA model on the log-transformed variable, adjusting for treatment group and age stratum (adolescents aged 12 to 17 or young adults aged 18 to 21). The least square geometric mean ratio will be provided with associated 90% CI.

The antibody response to the quadrivalent influenza vaccine strain is defined as a ≥ 4 -fold rise in HAI or a ≥ 4 -fold rise in MN from pre-dose antibody measure to post-dose antibody measure. The proportion of participants who experience a post-dose antibody response at Week 16 (EOT) for HAI and the proportion of participants who experience a post-dose antibody response at Week 16 (EOT) for MN and corresponding 90% Clopper-Pearson exact CIs will be summarized by treatment group and by strain.

The proportion of participants who achieve a post-dose HAI antibody titer ≥ 40 and the proportion of participants who achieve a post-dose MN antibody titer ≥ 40 at Week 16 (EOT) and corresponding 90% Clopper-Pearson exact CIs will be summarized by treatment group and by strain.

Secondary Endpoints

Tezepelumab serum concentrations will be summarized using descriptive statistics at each visit. ADA to tezepelumab will be summarized using descriptive statistics at each visit.

Safety Endpoints

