9 STATISTICAL CONSIDERATIONS

9.1 Statistical Hypotheses

No formal statistical hypotheses will be tested.

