9.4.2 Efficacy

All efficacy objectives will be evaluated for the double-blind treatment period, defined as the period after administration of randomized study intervention at Week 0 and the conclusion of Week 16 (EOT) Visit, inclusive.

The tezepelumab versus placebo humoral immune responses following seasonal influenza virus vaccination will be assessed by the following endpoints.

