3.3.1 General Study Level Definitions

Unless stated otherwise, continuous variables will be summarized by descriptive statistics (number of participants [n], arithmetic mean, standard deviation (SD), minimum, median and maximum). Categorical variables will be summarized in frequency tables (frequencies and percentages).

Mean(s), median(s), SD(s) and quartiles (where applicable) will be displayed with one more decimal place than the collected data. Minimum(s) and maximum(s) will be displayed with the same number of decimal places as the collected data. For discrete variables, population size (N for analysis set size and n for available data) and percentage will be presented. Percentages will be displayed with one decimal place.

As no statistical testing is planned, no p-values will be presented.

If influenza vaccine administration is delayed, an additional one to two study intervention doses may be administered to participants during unscheduled visits prior to visit 6 (as needed) until the influenza vaccine is available at study sites. Throughout this document End of Treatment (EOT) refers to the end of treatment visit, which is four weeks after the last dose of study intervention and could be either week 16, 20 or 24 for each participant. The end of study visit is 16 weeks after last dose of study intervention.

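### The four responder-type primary endpoints have no planned between-arm estimate or interval, only a proportion and 90% CI within each arm

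*SAP*

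**What the plan says.** SAP 4.2.1.1 gives the primary objective as to "evaluate the effect of tezepelumab on the humoral immune response following seasonal influenza virus vaccination" in this population. Protocol 9.4.2 introduces the efficacy endpoints as a comparison: "The tezepelumab versus placebo humoral immune responses following seasonal influenza virus vaccination will be assessed by the following endpoints". All eight primary endpoints follow that sentence.

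The eight are then handled in two ways.

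- **GMFR and GMT, by HAI and MN (four endpoints).** An ANCOVA on the log scale with treatment and age stratum gives a between-arm ratio. SAP 4.2.1.4: "The least square geometric mean ratio and mean difference will be provided with associated 90% CIs". Forest plots are planned for these results.
- **At least a 4-fold rise, and titer of at least 40, by HAI and MN (four endpoints).** SAP 4.2.1.4 gives the proportions, and "corresponding 90% Clopper-Pearson exact CIs will be summarized by treatment group". The responder summary measure in SAP Table 2 is "Number and % of participants in each treatment group meeting the specified threshold and corresponding 90% CI". Protocol Table 11 gives the same measure. The Protocol synopsis and 9.4.2.1 give the same analysis with the strain added: "corresponding 90% Clopper-Pearson exact CIs will be summarized by treatment group and by strain".

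Both documents rule out testing. Protocol 9.1: "No formal statistical hypotheses will be tested". SAP 3.3.1: "As no statistical testing is planned, no p-values will be presented".

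**The concern.** A percentage with an interval in each arm describes that arm; it does not estimate the effect of tezepelumab. For half of the primary endpoints the planned output therefore shows how well each arm's rate is known, but not how well the difference between arms is known. A reader left with two per-arm intervals can go wrong in either direction. Taking a per-arm half-width as the precision of the comparison overstates that precision. Judging by overlap can hide a difference that a proper interval would show, which matters in a study looking for an impaired vaccine response.

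The documents agree with each other, so this is not a contradiction. It is the same gap in five places, with no reason given for treating the two groups of endpoints differently.

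**Working it through.** **1. Is the contrast supplied elsewhere?** The mean difference and the forest plots in SAP 4.2.1.4 belong to the ANCOVA paragraph. The optional sensitivity analyses in SAP 4.2.1.5 change who is included and add no contrast. No other section gives a difference, ratio or odds ratio for the responder endpoints.

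**2. The plan's own precision figure.** Protocol 9.2 gives 50 per arm, SD 1.2 on the natural log scale, an observed ratio of 1 and a 90% CI of 0.67 to 1.48.

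- SE = 1.2 × √(2/50) = 0.240
- exp(±1.645 × 0.240) = 0.674 to 1.484

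The figure reproduces. It rests on a log-titer SD, so it says nothing about the responder rates. No precision figure is given for those.

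**3. What a between-arm interval would look like.** The responder rates below are assumptions. All intervals are two-sided 90% (z = 1.645), with equal observed counts in the two arms.

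- Clopper-Pearson, per arm: beta quantiles B(0.05; x, n−x+1) and B(0.95; x+1, n−x).
- Newcombe, difference: with equal counts the half-width is √[(p−l)² + (u−p)²], where l and u are the Wilson limits.
- Miettinen-Nurminen, difference: the values d that solve (p₁−p₂−d)/√V(d) = ±1.645. V(d) is the variance at the maximum-likelihood rates constrained to differ by d, times (n₁+n₂)/(n₁+n₂−1).

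Example, 35/50 in both arms:

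- Wilson centre (0.70 + 2.706/100)/(1 + 2.706/50) = 0.690
- Wilson half-width 1.645 × √(0.21/50 + 2.706/10000)/1.0541 = 0.104, so the limits are 0.585 and 0.794
- Newcombe half-width √(0.1146² + 0.0941²) = 0.148

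Half-widths in percentage points:

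| Assumed rate | n/arm | Per arm (Clopper-Pearson) | Difference (Newcombe) | Difference (Miettinen-Nurminen) |
|---|---|---|---|---|
| 30% or 70% | 50 | 11.4 | 14.8 | 15.1 |
| 40% or 60% | 50 | 12.1 | 15.7 | 16.0 |
| 50% | 50 | 12.4 | 16.0 | 16.3 |
| 80% | 50 | 10.1 | 13.2 | 13.4 |
| 90% | 50 | 7.9 | 10.5 | 10.6 |
| 50% | 40 (assumed) | 13.9 | 17.8 | 18.2 |
| 90% | 40 (assumed) | 9.0 | 11.8 | 12.1 |

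**4. Overlap can mislead.** Both cases have 50 per arm.

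- 35/50 vs 26/50: the per-arm intervals are 57.6 to 80.5% and 39.5 to 64.3%, which overlap. The Miettinen-Nurminen CI for the difference is +1.9 to +33.2 points.
- 45/50 vs 38/50: the per-arm intervals are 80.1 to 96.0% and 64.0 to 85.5%, which overlap. The CI for the difference is +1.7 to +26.6 points.

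**5. Does the method or the stratification matter much?**

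- At 30/50 vs 20/50, Newcombe gives 3.6 to 35.0 and crude Miettinen-Nurminen 3.5 to 35.5, at most 0.5 points apart.
- With 35/50 in both arms and 25 per arm in each age stratum, the crude half-width is 15.1. Stratified with weights n₁n₂/(n₁+n₂), it is 15.2, 15.1, 14.9, 14.2 and 13.2 for assumed age differences in response of 4, 12, 20, 36 and 52 points.

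**6. How many intervals?** H3N2 is measured by MN only (SAP 3.3.4). So (3 HAI strains + 4 MN strains) × 2 responder endpoints = 14. With no true effect, about 14 × 0.10 = 1.4 of these 90% intervals would exclude 0 on average.

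**The case against.** The best case against is about weight, and much of it stands.

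- **The crude interval can be recovered.** Counts and denominators by arm will be reported, so any reader can compute an unstratified difference and its interval. This is correct. It leaves the method to be chosen after the data are seen, and an age-stratified interval needs counts by stratum, which the plan does not call for.
- **Little turns on pre-specifying the method.** This is also correct: the two methods nearly agree, and stratification matters only if response differs strongly by age. The issue is the absent output more than the choice of method.
- **No decision depends on it.** There is no hypothesis, margin or p-value, the responder endpoints dichotomise the same titers, and the GMT and GMFR ratios already address the objective. This stands, and it is why the point is not critical.
- **Protocol 9.4.2 promises an assessment, not an effect estimate for each endpoint, and Protocol 9.2 concerns the GMT ratio only.** Both are literally true. Yet the only precision on which the sample size is justified is that of a between-arm estimate, and the no-testing rule did not stop the plan from giving one for the other four endpoints.
- **The rates are illustrative.** If titers of at least 40 are nearly universal, the intervals are narrower: at 48/50 in both arms the Miettinen-Nurminen half-width is 8.0 points. Unequal age strata hardly change the result: with 40 and 10 per arm and a 70% rate throughout, it is 15.2.

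**Conclusion.** The point holds. For four of the eight primary endpoints the planned summary measure describes each arm and does not compare them, although the stated objective is a treatment effect. The gap is the same in both documents and is not explained.

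With 50 per arm and assumed equal rates of 30% to 90%, the missing interval would have a half-width of 10.5 to 16.0 points (Newcombe) or 10.6 to 16.3 (Miettinen-Nurminen), against 7.9 to 12.4 for the planned per-arm intervals. With an assumed 40 per arm in the analysis set it would be 11.8 to 17.8 or 12.1 to 18.2, against 9.0 to 13.9. These sizes rest entirely on assumed rates and would be smaller for rates above 90%.

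This is a gap in the planned output, not a flaw that undermines the study. It should be fixed because doing so is cheap and because pre-specification is lost after unblinding.

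**What to change.** Before unblinding at the primary database lock, add to SAP 4.2.1.4:

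> For each strain and assay, the difference in responder proportion (placebo minus tezepelumab) will be presented with a 90% score-type CI stratified by the age randomization stratum (12 to 17, 18 to 21), using the stratified Miettinen-Nurminen method. These intervals are not adjusted for multiplicity and are estimates only; no p-value or decision rule is attached.

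Align the responder summary measure in SAP Table 2 and Protocol Table 11, and the text in Protocol 9.4.2.1 and the synopsis. Keep the per-arm Clopper-Pearson intervals as descriptive output. Stratification is proposed to match the randomization and the ANCOVA, not because a large gain in precision is expected.

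The cost is a short SAP edit, a protocol alignment that may be classed as an amendment, and 14 more estimates with intervals. About 1.4 of those would exclude 0 by chance if there were no effect, so the estimates-only statement is needed. No new data or participants are required. Protocol 9.4.1 allows SAP amendments up to unblinding; if that point has passed, the same output can be added but should be labelled post hoc.
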